### 7.1.2 Standard of Care Study Procedures

Wrist arthroscopy will be performed with regional anesthesia or general anesthesia, determined by the anesthesia team pre-operatively. An upper arm tourniquet will be used. Standard wrist arthroscopy tower will be used. Access to the joint for visualization, instrumentation, inflow, and outflow will use standard portals (see above).

### 7.2 Study Schedule

### 7.2.1 Screening

### Screening Visit (Day -28 to -1)

 During pre-operative clinical evaluation, the attending will determine potential study participants who are indicated for wrist arthroscopy and meet the inclusion criteria.

### 7.2.2 Enrollment/Baseline

### **Enrollment/Baseline Visit (Visit 1, Day 0)**

- Obtain informed consent of potential participant verified by signature on study informed consent form.
- Verify inclusion/exclusion criteria.
- Patient then undergoes wrist arthroscopy with the Arthrex NanoScope followed by conventional instruments (See section 7.1.1).

### 7.2.3 Intermediate Visits

There will be no intermediate visits.

### 7.2.4 Final Study Visit

There will be no final study visit.

Version: June 8, 2020

### 7.2.5 Withdrawal/Early Termination Visit

Following signing of the consent,, prior to the procedure, the patient is able to withdraw from the study...

### 7.2.6 Unscheduled Visit

As study participation takes place over a single day, unscheduled visit is not applicable.

### 7.3 Concomitant Medications, Treatments, and Procedures

All concomitant prescription medications taken during study participation will be recorded on the case report forms (CRFs). For this protocol, a prescription medication is defined as a medication that can be prescribed only by a properly authorized/licensed clinician. Medications to be reported in the CRF are concomitant prescription medications, over-the-counter medications and non-prescription medications.

### 7.4 Justification for Sensitive Procedures

The justification to for performing a diagnostic arthroscopy with the Arthrex NanoScope is to evaluate diagnostic accuracy as this device was intended for visualization of small joints and is currently in use and considered within standard of care.

### 7.4.1 Precautionary Medications, Treatments, and Procedures

Not applicable.

### 7.5 Prohibited Medications, Treatments, and Procedures

Treatment with additional upper extremity surgical procedures will not be permitted unless discussed with and approved by the principal investigator.

# 8 Assessment of Safety

### 8.1 Specification of Safety Parameters

### 8.1.1 Definition of Adverse Events (AE)

An **adverse event** (AE) is any symptom, sign, illness or experience that develops or worsens in severity during the course of the study. Intercurrent illnesses or injuries should be regarded as adverse events. Abnormal results of diagnostic procedures are considered to be adverse events if the abnormality:

- results in study withdrawal
- is associated with a serious adverse event
- is associated with clinical signs or symptoms
- · leads to additional treatment or to further diagnostic tests

### CONFIDENTIAL

Version: June 8, 2020

• is considered by the investigator to be of clinical significance

### 8.1.2 Definition of Serious Adverse Events (SAE)

### Serious Adverse Event

Adverse events are classified as serious or non-serious. A serious adverse event is any AE that is:

- fatal
- life-threatening
- · requires or prolongs hospital stay
- results in persistent or significant disability or incapacity
- a congenital anomaly or birth defect
- an important medical event

Important medical events are those that may not be immediately life threatening, but are clearly of major clinical significance. They may jeopardize the subject, and may require intervention to prevent one of the other serious outcomes noted above. For example, drug overdose or abuse, a seizure that did not result in in-patient hospitalization, or intensive treatment of bronchospasm in an emergency department would typically be considered serious.

All adverse events that do not meet any of the criteria for serious should be regarded as *non-serious adverse events*.

### 8.1.3 Definition of Unanticipated Problems (UP)

### **Unanticipated Problems Involving Risk to Subjects or Others**

Any incident, experience, or outcome that meets all of the following criteria:

- Unexpected in nature, severity, or frequency (i.e. not described in study-related documents such as the IRB-approved protocol or consent form, the investigators brochure, etc)
- Related or possibly related to participation in the research (i.e. possibly related means there is a reasonable possibility that the incident experience, or outcome may have been caused by the procedures involved in the research)
- Suggests that the research places subjects or others at greater risk of harm (including physical, psychological, economic, or social harm).

### 8.2 Classification of an Adverse Event

# 8.2.1 Severity of Event

For AEs not included in the protocol defined grading system, the following guidelines will be used to describe severity.

• Mild – Events require minimal or no treatment and do not interfere with the participant's daily activities.

### CONFIDENTIAL

Version: June 8, 2020

• **Moderate** – Events result in a low level of inconvenience or concern with the therapeutic measures. Moderate events may cause some interference with functioning.

• **Severe** – Events interrupt a participant's usual daily activity and may require systemic drug therapy or other treatment. Severe events are usually potentially life-threatening or incapacitating.

### 8.2.2 Relationship to Study Agent

For all collected AEs, the clinician who examines and evaluates the participant will determine the AE's causality based on temporal relationship and his/her clinical judgment. The degree of certainty about causality will be graded using the categories below.

- **Definitely Related** There is clear evidence to suggest a causal relationship, and other possible contributing factors can be ruled out. The clinical event, including an abnormal laboratory test result, occurs in a plausible time relationship to drug administration and cannot be explained by concurrent disease or other drugs or chemicals. The response to withdrawal of the drug (dechallenge) should be clinically plausible. The event must be pharmacologically or phenomenologically definitive, with use of a satisfactory rechallenge procedure if necessary.
- **Probably Related** There is evidence to suggest a causal relationship, and the influence of other factors is unlikely. The clinical event, including an abnormal laboratory test result, occurs within a reasonable time after administration of the drug, is unlikely to be attributed to concurrent disease or other drugs or chemicals, and follows a clinically reasonable response on withdrawal (dechallenge). Rechallenge information is not required to fulfill this definition.
- **Possibly Related** There is some evidence to suggest a causal relationship (e.g., the event occurred within a reasonable time after administration of the trial medication). However, other factors may have contributed to the event (e.g., the participant's clinical condition, other concomitant events). Although an AE may rate only as "possibly related" soon after discovery, it can be flagged as requiring more information and later be upgraded to "probably related" or "definitely related," as appropriate.
- Unlikely to be related A clinical event, including an abnormal laboratory test result, whose temporal relationship to drug administration makes a causal relationship improbable (e.g., the event did not occur within a reasonable time after administration of the trial medication) and in which other drugs or chemicals or underlying disease provides plausible explanations (e.g., the participant's clinical condition, other concomitant treatments).
- **Not Related** The AE is completely independent of study drug administration, and/or evidence exists that the event is definitely related to another etiology. There must be an alternative, definitive etiology documented by the clinician.

### 8.2.3 Expectedness

[name] will be responsible for determining whether an AE is expected or unexpected. An AE will be considered unexpected if the nature, severity, or frequency of the event is not consistent with the risk information previously described for the study agent.

### 8.3 Time Period and Frequency for Event Assessment and Follow-Up

The occurrence of an AE or SAE may come to the attention of study personnel during study visits and interviews of a study participant presenting for medical care, or upon review by a study monitor. All AEs including local and systemic reactions not meeting the criteria for SAEs will be captured on the appropriate RF. Information to be collected includes event description, time of onset, clinician's assessment of severity,

Version: June 8, 2020

relationship to study product (assessed only by those with the training and authority to make a diagnosis), and time of resolution/stabilization of the event. All AEs occurring while on study must be documented appropriately regardless of relationship. All AEs will be followed to adequate resolution.

Any medical condition that is present at the time that the participant is screened will be considered as baseline and not reported as an AE. However, if the study participant's condition deteriorates at any time during the study, it will be recorded as an AE. UPs will be recorded in the data collection system throughout the study.

Changes in the severity of an AE will be documented to allow an assessment of the duration of the event at each level of severity to be performed. AEs characterized as intermittent require documentation of onset and duration of each episode.

The PI will record all reportable events with start dates occurring any time after informed consent is obtained until 7 (for non-serious AEs) or 30 days (for SAEs) after the last day of study participation. At each study visit, the investigator will inquire about the occurrence of AE/SAEs since the last visit. Events will be followed for outcome information until resolution or stabilization.

All unresolved adverse events should be followed by the investigator until the events are resolved, the subject is lost to follow-up, or the adverse event is otherwise explained. At the last scheduled visit, the investigator should instruct each subject to report any subsequent event(s) that the subject, or the subject's personal physician, believes might reasonably be related to participation in this study. The investigator should notify the study sponsor of any death or adverse event occurring at any time after a subject has discontinued or terminated study participation that may reasonably be related to this study. The sponsor should also be notified if the investigator should become aware of the development of cancer or of a congenital anomaly in a subsequently conceived offspring of a subject that has participated in this study.

# 8.4 Reporting Procedures – Notifying the IRB

### 8.4.1 Adverse Event Reporting

Each adverse event will be reviewed on a case-by-case basis by the study physician and Principle Investigator to determine any risks to the participants' continued participation in the study.

There are no predefined stopping rules for the study. The following table will be used to document such adverse events:

Subject Name	Procedure Date	Signs of Adverse Event	Signature of Monitor	Date and Time

Adverse events will be reported to the IRB within 5 days of the event. Acute medical care will be provided as appropriately needed. The report will be submitted to the IRB on an adverse event CRF and an IRB reportable events form. If the subject reports their inability to continue the study, significant discomfort, or other negative effects, the procedure will terminate immediately, and any generated data will be destroyed. We do not anticipate any such adverse events as all pre-operative or post-operative assessments and interventions are standard of care.

Version: June 8, 2020

The data of adverse events under this monitoring plan will be assessed by the PI quarterly, every 3 months. Results and all adverse outcomes will be communication to the IRB by the Investigator when required. Every 12 months a review of all subject records, the progress of the study, any safety issues and adverse events that have occurred will be conducted and a report will be included during the annual IRB continuation review.

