### 5.7 Participant Withdrawal or Termination

### 5.7.1 Reasons for Withdrawal or Termination

Participants are free to withdraw from participation in the study at any time upon request. An investigator may terminate participation in the study if:

- Any clinical adverse event (AE), laboratory abnormality, or other medical condition or situation occurs such that participation in the study
  would not be in the best interest of the participant.
- The participant meets an exclusion criterion (either newly developed or not previously recognized) that precludes study participation.

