### 8.4.2 Serious Adverse Event Reporting

If an event occurs and is determined to be a SAE, it will be documented and monitored as described for AE's, with the addition that the Investigator will notify the IRB directly within 1 business day. Appropriate acute medical care will be provided to the subject.

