### 10.3.4 Safety Analyses

Safety endpoints will be analyzed as summary statistics during treatment. Adverse events will be PI reported. Adverse events leading to premature discontinuation from the study will be presented in a table.

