# 14 Data Handling and Record Keeping

### 14.1 Data Collection and Management Responsibilities

Data collection is the responsibility of the clinical trial staff at the site under the supervision of the site PI. The investigator is responsible for ensuring the accuracy, completeness, legibility, and timeliness of the data reported.

All source documents should be completed in a neat, legible manner to ensure accurate interpretation of data. Black ink is required to ensure clarity of reproduced copies. When making changes or corrections, cross out the original entry with a single line, and initial and date the change. DO NOT ERASE, OVERWRITE, OR USE CORRECTION FLUID OR TAPE ON THE ORIGINAL.

Copies of the electronic CRF (eCRF) will be provided for use as source documents and maintained for recording data for each participant enrolled in the study. Data reported in the eCRF derived from source documents should be consistent with the source documents or the discrepancies should be explained and captured in a progress note and maintained in the participant's official electronic study record.

Version: June 8, 2020

Clinical data (including AEs, concomitant medications, and expected adverse reactions data) and clinical laboratory data will be entered into a 21 CFR Part 11-compliant data capture system. The data system includes password protection and internal quality checks, such as automatic range checks, to identify data that appear inconsistent, incomplete, or inaccurate. Clinical data will be entered directly from the source documents.

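### Section 8.4.1 orders undefined generated data destroyed after a subject-reported negative effect; read literally, this conflicts with the plan's own adverse-event documentation and reporting

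*Combined protocol and SAP*

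**What the plan says.** Section 8.4.1 sets out how adverse events are recorded and reported. It supplies a table for documenting them and adds that "The report will be submitted to the IRB on an adverse event CRF and an IRB reportable events form". It then addresses a subject who reports being unable to continue, significant discomfort or other negative effects: "the procedure will terminate immediately, and any generated data will be destroyed". The sentence after that reads "We do not anticipate any such adverse events as all pre-operative or post-operative assessments and interventions are standard of care". The section goes on to require a quarterly assessment of adverse-event data by the principal investigator and a 12-monthly review of all subject records.

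Elsewhere the protocol requires adverse-event information to be kept and used:

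- Section 8.3: "All AEs occurring while on study must be documented appropriately regardless of relationship". Events are also to be followed to resolution.
- Section 10.3.4: "Adverse events leading to premature discontinuation from the study will be presented in a table".
- Section 5.7.1: the investigator may end participation if "Any clinical adverse event (AE), laboratory abnormality, or other medical condition or situation occurs" and continuing would not serve the participant's interest.
- Section 8.4.2: a serious event is handled by the same route; "it will be documented and monitored as described for" adverse events in general, with faster notice to the IRB.
- Section 14.1: "Clinical data (including AEs, concomitant medications, and expected adverse reactions data) and clinical laboratory data will be entered" into the data capture system.

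**The concern.** A destruction rule triggered by a complaint from the subject sits inside the section on adverse-event reporting. Its object, generated data, is not defined anywhere, and no section excludes safety records from it.

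If the term includes the adverse-event record, staff who follow the clause cannot also meet 8.3, and the discontinuation table in 10.3.4 loses the cases to which the clause applies. If the term covers only the research measurements, the safety counts are unaffected, but a participant's diagnostic data are still discarded because of something that happened during the procedure. Destruction cannot be undone, so the meaning has to be settled before a case arises.

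**Working it through.** No figure in the plan is in dispute and no arithmetic applies. The check is a reading of the sections against each other.

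**1. Are the triggering occurrences adverse events?** Yes, on the protocol's own terms. The sentence following the clause labels them so, and the definition in 8.1.1 covers any symptom or experience that develops or worsens during the study. Significant discomfort fits that definition.

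**2. Is there an exemption for safety records?** None was found in 8.3, 8.4.1, 8.4.2, 10.3.4, 13.5, 14.1 or 14.2.

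**3. Broad reading: the term includes the adverse-event record.**

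| Section | Requires | Compatible with destruction? |
|---|---|---|
| 8.3 | Every on-study event documented and followed | No |
| 8.4.1 | Adverse-event form and IRB report | No |
| 8.4.1 | Quarterly assessment of adverse-event data; 12-monthly review of all subject records | No |
| 10.3.4 | Table of events leading to discontinuation | No, for the cases the clause reaches |

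Section 5.7.1 makes an adverse event a ground for ending participation, so the table in 10.3.4 would be expected to hold cases that overlap with those in the clause. The overlap is partial: 5.7.1 concerns a decision by the investigator, whereas the clause starts from a report by the subject.

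**4. Narrow reading: the term covers only scope assessments and the questionnaire.** The four conflicts in the table largely disappear. What remains is the loss of research data. Under 4.1 and 7.1.1 the NanoScope examination comes first, so its findings and the intended treatment can already exist when a procedure is stopped. If the stop comes before the conventional examination, there is no reference result, and that participant could not enter the accuracy comparison anyway. The NanoScope findings would still have belonged in the individual listing under 10.3.7. If the stop comes after both examinations, a complete pair is lost.

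**5. Does the wording choose between the readings?** No. Section 14.1 counts adverse events among clinical data, and 8.4.1 itself speaks of adverse-event data, which allows the broad reading. The separate adverse-event forms and the quarterly review presuppose that those records survive, which favors the narrow one.

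**6. How often could it apply?** The documents give no rate. The clause needs a subject who can report a complaint while there is a procedure to stop. Section 7.1.2 allows general anesthesia, under which the subject cannot report, and regional anesthesia, under which the subject may. The trigger is therefore possible but probably rare.

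**The case against.** The strongest defense is that this is an ambiguity and not a contradiction. The clause speaks of ending the procedure, so the natural referent is the data which that procedure produced. Adverse events go onto separate forms, which the same section orders just before the clause, and the later reviews assume those forms still exist. This carries weight: the conflict with adverse-event documentation holds only on the broad reading. It does not remove the point, because the text never states the narrow reading, and the narrow reading still has data destroyed because of an event during the procedure.

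Several stronger inferences are tempting, and the documents do not support them:

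- *That the safety tables as a whole would be emptied.* Events seen by clinicians without a complaint from the subject fall outside the clause. So do events arising after surgery within the 7-day (non-serious) or 30-day (serious) recording window of 8.3.
- *That serious events are expressly to be destroyed.* Section 8.4.2 carries over the documentation and monitoring of adverse events. It does not clearly import the destruction clause.
- *That 13.5 and 14.2 are flatly contradicted.* Section 13.5 has a different trigger, revocation of authorization. Section 14.2 bars destruction without the sponsor's consent only if applicable. Both sit awkwardly beside the clause and go no further.
- *That the number enrolled would be lost.* Signed consents are stored under 13.3.2 and 13.5.
- *That the primary accuracy estimate is shown to be biased.* No section gives a frequency from which to judge this.

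A reader might also want to add a safety denominator of participants whose procedure was started, or to rewrite the withdrawals line in 10.4. Neither is needed here. That denominator would clash with 8.3, which records events from informed consent onward, and it would leave no place for investigator terminations before surgery under 5.7.1.

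**Conclusion.** The point holds in a limited form. Section 8.4.1 contains a destruction rule whose object is undefined and from which safety records are not exempted. On a literal reading it cannot be reconciled with 8.3, 10.3.4 or the reporting and review steps of 8.4.1. On the narrower reading the safety record survives, and the defect is the irreversible removal of diagnostic data because of an event during the procedure.

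Confidence is high that the text needs correcting under either reading; which reading was intended cannot be settled from the documents. No numerical effect on the safety tables or on the accuracy estimate is claimed. That the trigger is rare is an inference from the setting and not a figure in the plan. The clause should be corrected, but nothing here shows that the study's conclusions would change.

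**What to change.** In 8.4.1, delete the words that order data to be destroyed. In their place state that the adverse-event record and all study data collected up to the point of stopping are retained, listed under 10.3.7 and reported under 10.3.4, and that revocation of authorization continues to be handled under 13.5. This removes the conflict under both readings. It takes no position on when a procedure should stop.

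The cost is one deleted clause and one short statement in an amendment, which needs IRB approval under 13.2. The consent form needs a matching change only if it repeats the clause. No visit, assessment or chart review is added.
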